6.2.12. Description of activities performed by Sponsor Representatives

A physician proctor and SJM Field clinical Specialist (FCS) will attend all proctored procedures to answer device and procedural questions, until the implanting investigator is deemed trained and he and his team are ready for independence. Physician training and proctoring will be documented appropriately.

It is permissible that a FCS will periodically attend procedures throughout the investigational study to observe the implanting investigator and his team. This will afford the opportunity for continued training if required and allow the investigator continued product support from the sponsor.

Sponsor personnel will not:

- Perform the informed consent process
- Practice medicine or participate directly in the procedure
- Provide medical diagnosis or treatment to patients
- Discuss a patient's condition or treatment with a patient
- Independently collect clinical investigational data or complete study documentation

6.2.13. Description of post-investigational provision of medical care

When the patient's participation in the clinical investigation has been completed the patient will return to medical care as per physician's recommendation.

7 Clinical Investigation Conduct

7.1 Statements of Compliance

The investigation will be performed in accordance with the most current versions of the World Medical Association (WMA) Declaration of Helsinki and any regional and/or national regulations as appropriate.

ISO14155 2011 shall be used as a guideline with following exceptions: limited adverse event reporting and device accountability.

The investigator shall not start enrolling patients or requesting informed consent prior to obtaining EC approval and national competent authority/national regulatory authority approval, if applicable, and authorization from the sponsor in writing for the investigation. In case additional requirements will be imposed by the EC or national competent authority/national regulatory authority they shall be followed, if appropriate.

As sponsor, SJM has taken up general liability insurance in accordance with the requirements of the applicable local laws. If required, additional patient coverage or an investigation specific insurance shall be provided by the Sponsor as well.

7.1.1. Adherence to the Clinical Investigation Plan

The principal investigator and delegates are required to adhere to the CIP in order to prevent patients from being exposed to unreasonable risks. In addition, the principal investigator and delegates are required to be compliant with the signed clinical investigation agreement, applicable national or local laws and regulations, and any conditions required by the appropriate EC or applicable regulatory authorities are expected as well. Instances of failure, intentionally or unintentionally, to adhere to the requirements of the CIP are considered a deviation.

In some cases failure to comply with the protocol may be considered failure to protect the rights, safety and well-being of patients, since the non-compliance exposes patients to unreasonable risks. For example, failure to adhere to the inclusion/exclusion criteria: these criteria are specifically defined by the sponsor to exclude patients for whom the investigational device is not beneficial and the use involves unreasonable risks. This may be considered failure to protect the rights, safety and well-being of the enrolled patient. Similarly, failure to perform safety assessments intended to detect adverse events may be considered failure to protect the rights, safety and well-being of the enrolled patient. Investigators should seek minimization of such risks by adhering to the protocol.

Simultaneously, in the event that adhering to the protocol might expose the patient to unreasonable risks, the investigator is also required to protect the rights, safety and well-being of the patient by intentionally deviating from the requirements of the CIP, so that patients are not exposed to unreasonable risks.

It is the responsibility of the investigator to provide adequate medical care to a patient enrolled in an investigation.

The PI shall promptly report to the sponsor any deviations from the CIP that affect the rights, safety or well-being of the patient or the scientific integrity of the clinical investigation, including those which occur under emergency circumstances. The reporting of these deviations should be done as soon as

possible but no later than 72 hours after the investigator becomes aware. The investigator shall also notify promptly the EC, as per their requirements. Any corrective and preventive actions required by the EC must be complied with by the site.

The sponsor will notify the national competent authorities/national regulatory authorities and EC as per their requirements.

7.1.2. Repeated non-compliance

In the event of repeated non-compliance or a serious non-compliance, as determined by the sponsor, a clinical research associate or a clinical representative will attempt to secure compliance by one or more of the following actions:

- Contacting the investigator by telephone
- Contacting the investigator in writing
- Visiting the investigator
- Retraining of the investigator
- Site “for-cause” audit
- Implementation of corrective action preventive action (CAPA) plan

If an investigator is found to be repeatedly non-compliant with the signed clinical investigation agreement, the CIP or any other conditions of the clinical investigation, the sponsor will either secure compliance or, at its sole discretion, terminate the investigator’s participation in the clinical investigation.

7.2 Informed Consent Process

7.2.1. General Process

Provision of the informed consent is mandatory. Informed consent is required from all patients (or their legal representatives) prior to participation in the clinical investigation. The process of obtaining informed consent shall comply with the most recent version of the declaration of Helsinki, ISO 14155 2011 and all applicable regulations.

The principal investigator or his/her authorized designee will conduct the informed consent process. This process will include a verbal discussion with the patient on all aspects of the clinical investigation that are relevant to the patient’s decision to participate in the clinical investigation. It is crucial that this discussion is documented in the source documents (records of the patient).

The patient will be provided with the informed consent form that is written in native non-technical language, understandable for the patient, and has been approved by EC. The patient is given ample time to consider participation and ask questions if necessary.

In order to avoid any possible coercion or undue improper influence on, or inducement of the patient to participate, the sponsor requests the investigator to only sign the informed consent form once the patient has signed and dated the document and therefore decided to participate in the investigation.

Informed consent of a patient shall always be indicated by personally dated signature of the patient and by the investigator responsible for conducting the informed consent process. It is crucial that the signature of the informed consent is documented in the source documents (records of the patient).

One original signed consent document must be retained on file by the investigator and a copy of the signed and dated consent is provided to the patient (investigator's responsibility).

The patient's legal rights will not be waived nor the appearance that these will be waived. Important new information that becomes available throughout the clinical investigation will have to be provided in writing to new and existing patients. If relevant, all affected patients shall be asked to confirm their continuing informed consent in writing.

NOTE: In certain circumstances, it might be decided during screening to send relevant clinical data (such as echocardiogram, CT/MRI or Angiogram) out of the hospital for further analysis to determine if patient's valve anatomy is suitable for participation in the clinical investigation. If required, an authorization form to release medical information outside the hospital is available for sign-off by the patient. In case this authorization form is signed by the patient, the patient is not yet considered enrolled.

7.2.2. Patient unable to read or write

Informed consent shall be obtained through a supervised oral process if a patient or legally authorized representative is unable to read or write. An independent witness shall be present throughout the process. The written informed consent form and any other information shall be read aloud and explained to the prospective patient or his/her legally authorized representative and, whenever possible, either shall sign and personally date the informed consent form. The witness also signs and personally dates the informed consent form attesting that the information was accurately explained and that informed consent was freely given.

7.3 Adverse Event, Adverse Device Effect, Device Deficiency

7.3.1. Definitions (ISO 14155:2011)

Medical device

Any instrument, apparatus, implement, machine, appliance, implant, software, material or other similar or related article

- Intended by the manufacturer to be used, alone or in combination, for human beings for one or more of the specific purpose(s) of
 - Diagnosis, prevention, monitoring, treatments or alleviation of disease,
 - Diagnosis, monitoring, treatment, alleviation of, or compensation for, an injury,
 - Investigation, replacement, modification, or support of the anatomy or of a physiological process,
 - Supporting or sustaining life,
 - Control of conception,
 - Disinfection of medical devices and
- Which does not achieve its primary intended action in or on the human body by pharmacological, immunological or metabolic means, but which may be assisted in its intended function by such means

Adverse Event (AE)

Any untoward medical occurrence, unintended disease or injury, or untoward clinical signs (including abnormal laboratory findings) in patients, users or other persons, whether or not related to the medical device.

This definition includes events related to the medical device or the comparator.

This definition includes events related to the procedures involved.

Serious Adverse Event (SAE)

An adverse event that led to:

- Death
- A serious deterioration in the health of the patient, that either resulted in:
 - A life-threatening illness or injury OR
 - A permanent impairment to a body structure or a body function OR
 - An in-patient or prolonged hospitalization OR
 - A medical or surgical intervention to prevent life-threatening illness or injury or permanent impairment to a body structure or a body OR
 - A malignant tumor
- Fetal distress, fetal death or a congenital abnormality or birth defect

A planned hospitalization for a pre-existing condition, or a procedure required by the CIP is not considered a serious adverse event.

Adverse Device Effect (ADE)

An adverse event related to the use of a medical device

This definition includes adverse events resulting from insufficient or inadequate instructions for use, deployment, implantation, installation, or operation, or any malfunction of the medical device.

This definition includes any event resulting from the use error or from intentional misuse of the medical device.

Serious Adverse Device Effect (SADE)

Adverse device effect that has resulted in any of the consequences characteristic of a serious adverse event.

Unanticipated Serious Adverse Device Effect (USADE)

A serious adverse device effect which by its nature, incidence, severity or outcome has not been identified in the current version of the risk analysis report.

Anticipated Serious Adverse Device Effect (ASADE)

A serious adverse device effect which by its nature, incidence, severity or outcome has been previously identified in the risk analysis report.

Device Deficiency (DD)

An inadequacy of a medical device with respect to its identity, quality, durability, reliability, safety or performance. Device Deficiencies include malfunctions, use errors and inadequate labeling.

7.3.2. Procedure for assessing, recording and reporting adverse events, adverse device effects, serious adverse events, serious adverse device effects and device deficiencies

Safety surveillance and reporting will be done for all patients enrolled in this investigation.

Safety surveillance within this clinical investigation and safety reporting, both performed by the investigator, starts as soon as the patient is enrolled in this clinical investigation (date of signature of the informed consent). The safety surveillance and the safety reporting will continue until the last investigational visit has been performed or the patient is deceased or the patient/investigator concludes his participation into the clinical investigation.

NOTE: If an adverse event is documented at the patient's last follow up visit, both the notification and follow-up information on the AE eCRF are to be provided to the sponsor.

- All Serious Adverse Events (regardless of their relationship with the device or the procedure) and all Adverse Device Effects (serious or non-serious) are to be documented and reported to the sponsor maximum 3 calendar days after becoming aware of the event.
- All Device Deficiencies, that could have led to a Serious Adverse Device Effect,
 - if either suitable action had not been taken;
 - if intervention had not been made or
 - if circumstances had been less fortunate,are to be documented and reported to the sponsor maximum 3 calendar days after becoming aware of the event.
- Non-serious adverse events documentation and reporting are limited to cardiovascular and neurovascular events; they all have to be reported regardless of their relationship with the device or the procedure.

7.3.3. Should an AE or DD occur, record AE or DD information in the hospital records, document the information into the adverse event form or device deficiency form as soon as possible. By completing the form, the sponsor will be notified. Refer to

and Appendix C: Data Collection Method. In case of EDC failure, notify Sponsor via Fax or via [contact].

The Sponsor safety department will be responsible for ensuring the assessment of immediate AE and DD ‘reportability’ or ‘non-reportability’ to the national competent authorities/national regulatory authorities. All the AEs and DDs will be documented and reported in periodic report(s) as per local requirements.

Additional information may be requested, when required, by the sponsor in order to support the reporting of AEs or DDs to regulatory authorities and to support AE or DD analysis. The investigator must notify the EC, if appropriate, in accordance with national and local laws and regulations, of the AEs and DDs reported to the sponsor.

In case of disagreement between sponsor and investigator in the AE or DD assessment, then both assessments will be reported.

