5.3.2 Secondary Endpoints

- Evaluation of the VARC-2¹⁹ defined event rates at 30 days, 1 year and annually through 5 years post implant. Definitions are detailed in Appendix D: VARC 2 Endpoints Definitions.
 - All-Cause Mortality
 - Cardiovascular Mortality
 - Myocardial Infarction
 - Stroke (disabling and non-disabling)
 - New or worsened conduction disturbances and cardiac arrhythmias (including pacemaker implantation rate at 30 days and new-onset atrial fibrillation (AF))
- Evaluation of the VARC-2¹⁹ defined event rates at 30 days from the index procedure.
 - Vascular access site complication (major and minor)
 - Bleeding (life-threatening, major and minor)
 - Acute kidney injury

- Prosthetic valve function at 30 days, 1 year and annually through 5 years post implant. (Includes prosthetic valve stenosis and prosthetic valve regurgitation).
- Clinical benefit endpoints at 30 days, 1 year and annually through 5 years post implant (if available)
 - NYHA functional classification
 - 6 Minute Walk Test (6MWT)
 - Quality of life measured with EQ-5D questionnaire through 1 year post-implant
- Evaluation of the TAVI-related resource utilization through hospital discharge (e.g. index procedural hospital/physician resources)
- Interim reporting at 30 days and 1-year all-cause mortality data may be performed on a subset of patients and compared with an appropriate external comparator. The results will be presented to appropriate agencies in France and in other countries where it will be deemed necessary for reimbursement purposes.

NOTE: Should new VARC or ESC Guidelines be published, endpoint analysis would be adjusted accordingly and analyzed to the extent that the previously gathered data supports the analyses based on the most current guidelines.

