
Portico Valve Implant (NAP for Cohort B)
	
Procedural information must be collected including:
 
 • Pre-implant information (such as access type, use of balloon valvuloplasty, etc.) • Implant information (such as prosthetic valve information, use of rapid pacing, etc.) • Aortic regurgitation • Implant depth and prosthesis-patient mismatch • Post-implant information including hemodynamics 
The assessment of aortic regurgitation must be performed with a combination of echocardiography, angiography and hemodynamic approach, preferably according to the instructions provided in Appendix I: Peri-procedural instructions.
 
Implant depth measurement should be assessed via aortic root angiography and further instructions are also provided in Appendix I: Peri-procedural instructions.
 
Prosthesis-patient mismatch will be measured by means of echocardiography according to the VARC 2 guidelines.

Study activities	Definitions
	Any other data acquired as part of the patient's implant procedure (such as routinely performed aortography) can be collected by the Sponsor as well to obtain additional procedural information regarding the implant.
Adverse Events Assessment (From 1Y visit onward for Cohort B)	All adverse events will be documented according to Section 7.3 (Adverse Events, Adverse Device Effect, and Device Deficiency).
Device Deficiency Assessment	All device deficiencies will be documented according to Section 7.3 (Adverse Events, Adverse Device Effect, and Device Deficiency).
Paced Rhythm Assessment (NAP for Cohort B)	If the patient received a new permanent pacemaker, due to an AV-block, within 30 days after their TAVI procedure, then the patient's dependence to pacemaker will be checked according to the recommendations provided in Appendix J: Recommendation for paced rhythm assessment in patients with a TAVI related implantation of permanent pacemaker.
Resource utilization Assessment (until discharge for COHORT A) (NAP for Cohort B)	Procedural resources: Material resources such as devices used during the procedure (valve, guiding catheters, valvuloplasty balloons, etc.), operators' resources and procedure duration will be collected at procedure time. Hospital resources: length of stay in different wards (ICU, non ICU, etc.); will be collected at discharge.

Table 4: Data Collection Forms for COHORT A and COHORT B (identical to Cohort A with exception of grey background boxes)

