14.3.2 Clinical Event Committee

An independent clinical events committee will be established for this clinical investigation. The CEC will include, at a minimum, an interventional cardiologist or a cardiologist, and a cardiothoracic surgeon whose main objective is to review and adjudicate specific adverse events which will occur throughout the duration of this trial, as specified in a separate CEC charter. The CEC will adjudicate these safety related events according to the VARC 2 criteria.

The CEC charter will be established for the CEC member's activities and will be available upon request.

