
Bleeding (VARC 2)
	
Life-threatening or disabling bleeding
 
 • Fatal bleeding (BARC(22) type 5) OR • Bleeding in a critical organ, such as intracranial, intraspinal, intraocular, or pericardial necessitating pericardiocentesis, or intramuscular with compartment syndrome (BARC type 3b and 3c) OR • Bleeding causing hypovolemic shock or severe hypotension requiring vasopressors or surgery (BARC type 3b) OR • Overt source of bleeding with drop in hemoglobin ≥ 5 g/dl or whole blood or packed red blood cells (RBCs) transfusion ≥ 4 Units^a (BARC type 3b). 
^aGiven 1 U of packed RBC typically will raise blood hemoglobin concentration by 1 g/dl, an estimated decrease in hemoglobin will be calculated.
 
Major bleeding (BARC type 3a)
 
 • Overt bleeding either associated with a drop in the hemoglobin level of at least

	
3.0 g/dl or requiring transfusion of two or three units of whole blood/ RBC, or causing hospitalization or permanent injury, or requiring surgery AND
 
 Does not meet criteria of life-threatening or disabling bleeding 
Minor bleeding (BARC type 2 or 3a, depending on the severity)
 
 Any bleeding worthy of clinical mention (e.g., access site hematoma) that does not qualify as life-threatening, disabling or major.

Acute Kidney Injury AKIN classification (VARC 2)
	
Stage 1 Increase in serum creatinine to 150% - 199% (1.5 to 1.99 X increase compared with baseline) OR increase of ≥ 0.3 mg/dl (≥ 26.4 mmol/l) OR Urine output <0.5 mL/kg/h for >6h but <12h
 
Stage 2 Increase in serum creatinine to 200% -299% (2.0 to 2.99 X increase compared with baseline) OR Urine output <0.5 mL/kg/h for >12h but <24h
 
Stage 3 Increase in serum e to $\geq 300\%$ (> 3 X increase compared with baseline) or serum creatinine of ≥ 4.0 mg/dl (≥ 354 mmol/l) with an acute increase of at least 0.5 mg/dl (44 mmol/l) OR Urine output <0.3 mL/kg/h for ≥ 24h OR Anuria for ≥ 12h
 
Patients receiving renal replacement therapy are considered to meet Stage 3 criteria irrespective of other criteria.

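### The limit on non-serious adverse event reporting leaves some acute kidney injury and minor-bleeding endpoint events outside what sites must report

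*Combined protocol and SAP*

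**What the plan says.** **Reporting rule.** Section 7.3.2 has three routes by which an adverse event must reach the sponsor:

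- all serious adverse events;
- device effects: "all Adverse Device Effects (serious or non-serious) are to be documented and reported to the sponsor";
- for everything else, "Non-serious adverse events documentation and reporting are limited to cardiovascular and neurovascular events".

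Section 7.3.1 defines an adverse device effect as "An adverse event related to the use of a medical device". The adverse event row of Table 3 (Section 6.2) adds no wider duty at visits, since it refers back to the same section: "All adverse events will be documented according to Section 7.3". The restriction is deliberate. Section 7.1 states: "ISO14155 2011 shall be used as a guideline with following exceptions: limited adverse event reporting and device accountability".

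**Endpoints.** Section 5.3.2 lists, among the event rates at 30 days from the index procedure, "Bleeding (life-threatening, major and minor") and acute kidney injury, the latter with no stage restriction. Appendix D grades AKI in three stages. A creatinine rise of 0.3 mg/dl is enough for stage 1. It defines minor bleeding as "Any bleeding worthy of clinical mention (e.g., access site hematoma) that does not qualify as life-threatening, disabling or major".

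**Adjudication and analysis.** Under Section 14.3.2 the CEC is to "review and adjudicate specific adverse events which will occur throughout the duration of this trial", with its scope set in a separate charter. Section 9.4 measures time from implant to first event, or to the last documented contact where there was no event.

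**The concern.** The reporting rule sorts events by seriousness, device relationship and body system. The endpoint definitions sort them by VARC-2 criteria. The two do not match, and no section says that an endpoint event must be reported whatever its seriousness or organ class.

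A transient stage 1 creatinine rise, or a minor urinary or gastrointestinal bleed not attributed to the device, meets an endpoint definition but none of the three reporting routes. A site can follow the protocol exactly and still leave such an event out of the data. The endpoint rate would then depend partly on how each site applies the word cardiovascular, which is not defined for this purpose. At stake is the validity of two 30-day safety rates that will carry VARC-2 labels. Only Cohort A is affected, because Cohort B patients enter at 1 year or later.

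**Working it through.** The plan gives no AKI rate, minor-bleeding rate or capture fraction, so it has no figure to reproduce. The check is mainly textual.

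**Step 1: does each event type have a mandatory route under 7.3.2?**

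| Endpoint event (Appendix D) | Serious event route | Device effect route | Cardiovascular/neurovascular route |
|---|---|---|---|
| AKI, serious (e.g. prolongs hospitalization) | Yes | – | – |
| AKI, non-serious, attributed to the device | No | Yes | – |
| AKI, non-serious, not attributed to the device | No | No | No (renal) |
| Access-site hematoma, non-serious | No | Possibly | Plausibly, at the site's discretion |
| Minor bleed at a remote, non-vascular site, not attributed to the device | No | No | No |

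The third and fifth rows are the gap. It is not confined to stage 1: a stage 2 AKI that meets no seriousness criterion falls in the same place.

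**Step 2: do other data sources in the plan recover these events?**

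- *Creatinine.* Table 2 schedules it at baseline, pre-discharge, 30 days and 1 year, but only where available, and Table 3 repeats that condition. Section 6.2.4 lists the pre-discharge sample without the condition, as one draw on day 2 to 4 or at discharge. One draw can miss a peak. Most of the creatinine criteria are also relative to baseline, and Section 6.2.2 keeps the availability condition for the baseline value. The 30-day list in Section 6.2.5 names only serum albumin, although Table 2 marks creatinine then.
- *Urine output.* Appendix D allows AKI to be met on this criterion alone. It is not scheduled.
- *Hemoglobin.* The minor-bleeding definition has no hemoglobin threshold, so a hemoglobin value cannot by itself identify a minor bleed.
- *Unscheduled visits.* Section 6.2.11 requires endpoint-related data from these visits to be documented. It does not naturally cover the index stay.
- *Forms.* Table 4 names no form dedicated to VARC-2 events. It lists form titles and not fields, so other forms may carry such items.
- *Derivation rule.* No section says that AKI or bleeding is derived from laboratory values.

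The backstops are real but partial.

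**Step 3: direction.** Under 9.4 a patient whose event was not recorded stays at risk until last contact. The event leaves the numerator and the patient stays in the risk set, so the estimated 30-day rate falls. With true rate r, share s of endpoint events in the gap, and share c of those recovered by another route:

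observed rate = r × [1 − s × (1 − c)]

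This never exceeds r, and equals r only if s = 0 or c = 1.

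**Step 4: illustration only.** All three inputs below are assumptions with no source in the documents.

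| Assumed r | Assumed s | Observed, c = 0 | Observed, c = 0.5 |
|---|---|---|---|
| 5% | 0.25 | 3.75% | 4.38% |
| 5% | 0.75 | 1.25% | 3.13% |
| 10% | 0.25 | 7.5% | 8.75% |
| 10% | 0.75 | 2.5% | 6.25% |
| 20% | 0.25 | 15% | 17.5% |
| 20% | 0.75 | 5% | 12.5% |

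For example, 10% × [1 − 0.25 × (1 − 0)] = 7.5%. The table shows how the result depends on s and c. It does not estimate the bias in this study.

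**The case against.** The strongest case against has four parts.

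*The gap is narrow.* Serious events, including those that prolong hospitalization, and all device effects remain reportable. Many access-site bleeds would probably be reported as cardiovascular or as device effects. Section 5.3.2 does not name stage 1 AKI: it enters through Appendix D, whose early-safety composite counts only stages 2 and 3. Most of this stands and limits the point to the two rows in Step 1. The composite is no answer, because 5.3.2 lists AKI and minor bleeding in their own right.

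*Unseen documents may close the gap.* The CEC charter, the eCRF fields and the separate statistical analysis plan mentioned in 9.4 are not available here. A reader might infer that these events never reach adjudication, or that the CEC never looks at laboratory data. The documents do not support either statement. They show only that the plan itself contains no such step. They also do not show that sites are forbidden to report. The safer reading is that reporting is not required.

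*Limited reporting is a declared choice.* Section 7.1 says so, and for general adverse events that is the sponsor's decision. It does not explain why events chosen as endpoints should fall under the limit.

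*No planned analysis turns on these rates.* A reader might infer that under-capture would flatter the device against published VARC-2 rates. The only external comparison in 5.3.2 concerns all-cause mortality. No AKI or bleeding comparison, hypothesis or performance goal is planned, so that inference goes beyond the documents.

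**Conclusion.** The point holds in a limited form. Sections 7.3.2 and 5.3.2 with Appendix D do not match: a non-serious AKI or a minor non-vascular bleed, neither attributed to the device, is an endpoint event that sites are not required to report. The plan's own backstops recover some AKI and few minor bleeds. Any loss that remains biases the 30-day AKI and minor-bleeding rates downward, and the loss may differ between sites.

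The size cannot be computed from the documents, and no particular fraction of lost events should be quoted as a finding. The conclusion assumes that the charter and eCRF do not already require these events to be collected. If they do, 7.3.2 still needs to be brought into line with them. The primary endpoint is unaffected. This should be corrected, but it does not threaten the main result.

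**What to change.** 1. Add to Section 7.3.2 that every event meeting an Appendix D definition of a secondary endpoint, including AKI of any stage and bleeding of any grade through 30 days, is reported on the adverse event form regardless of seriousness, relatedness or organ class, and is sent to the CEC. The general limit on other non-serious events can stay.
2. State in Section 9.4 or the separate analysis plan that creatinine-based AKI is also derived from the scheduled baseline, pre-discharge and 30-day values where available.
3. Check that the CEC charter and the eCRF agree with the new wording.

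The cost is site retraining and some extra adverse event forms, mostly in the first 30 days after implant. Sample size and the primary analysis do not change.
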